2.3.2.4 Mini Mental State Exam Total Score

The Mini Mental State Exam (MMSE) is being used in the study as a measure of cognition. The MMSE comprises 11 items assessing a patient's mental status and the individual's general level of impairment in five areas: orientation, short-term memory retention, attention, short-term recall, and language. The total score is calculated by summing scores of all 11 items. If any item score is missing or invalid, the item score will

be set to 0. The total score ranges from 0 – 30 with lower values indicating greater impairment.

2.3.3 Exploratory Efficacy Outcome Measures

2.3.3.1 Time to clinically evident decline

Time to clinically evident decline, as determined by:

- Confirmed decline of ≥ 2 points (at two consecutive visits) on the MMSE, AND
- Loss of ≥ 1 points on one or more basic ADL, as measured on the ADCS-ADL
OR
- Loss of ≥ 2 points on one or more iADL, as measured on the ADCS-ADL

2.3.4 Safety Outcome Measures

- Incidence and nature of MRI safety findings: ARIA-E and ARIA-H
- Incidence, nature, and severity of serious adverse events
- Incidence, nature, and severity of adverse events
- Incidence of treatment discontinuations due to adverse events
- Mean changes in clinical laboratory tests from baseline over time and incidence of abnormal laboratory values and abnormal laboratory values reported as adverse events
- Mean changes in ECG assessments from baseline over time and incidence of abnormal ECG assessments
- Incidence of anti-gantenerumab antibodies
- Physical and examination abnormalities
- Mean change in vital signs assessment from baseline over time and incidence of abnormal vital signs measurements

- Suicidal ideation, suicidal behavior, and self-injurious behavior without suicidal intent, as determined using the Columbia–Suicide Severity Rating Scale (C-SSRS)

2.3.5 Biomarker Outcome Measures

- Change from baseline in t-tau levels in cerebrospinal fluid (CSF) measured by the Elecsys® Total-Tau immunoassay
- Change from baseline in p-tau levels in CSF measured by the Elecsys® Phospho-Tau immunoassay
- Change from baseline in A β_{1-42} levels in CSF measured by the Elecsys® β -Amyloid (1-42) immunoassay
- Change from baseline in A β_{1-40} levels in CSF measured by the Elecsys® β -Amyloid (1-40) immunoassay
- Change from baseline in the A β_{1-42} / A β_{1-40} ratio in CSF
- Change from baseline in the pTau / tTau ratio in CSF
- Change from baseline in the pTau / A β_{1-42} ratio in CSF
- Change from baseline in A β_{1-42} levels measured by PET scan
- The change from baseline in hippocampal volume measured by MRI scan
- The change from baseline in whole brain volume measured by MRI scan
- The change from baseline in ventricular volume measured by MRI scan

2.3.6 Pharmacokinetic Outcome Measures

- Primary population PK parameters (e.g., apparent total CL [CL/F] and apparent volume of distribution [V/F]) and relevant covariates as necessary to describe the plasma gantenerumab concentration–time course
- Secondary population estimates of plasma gantenerumab exposure at steady state to include peak plasma concentration (C_{max}), time to peak concentration (T_{max}), trough plasma concentration (C_{min}), and AUC

2.3.7 Protocol Deviations

- Major protocol deviations summarized by four main categories (inclusion criteria, exclusion criteria, medication and procedural).

2.4 DETERMINATION OF SAMPLE SIZE

The sample size for this study was planned to be 500 patients per arm (Gantenerumab and Placebo). This calculation was based on the following assumptions:

Test	Two-sided
Alpha	0.05
Power	80%
Expected difference between treatment arms in absolute change from baseline at Week 104 in ADAS-Cog 13 (SD)	2.3 (10.4)
Expected difference between treatment arms in absolute change from baseline at Week 104 in ADCS-ADL (SD)	2.5 (10.9)
Expected withdrawal rate	30%

However, due to the conversion of study WN28745 to an OLE, recruitment into Part 1 of the study was stopped early. Final numbers recruited, enrolled and dosed in study WN28745 will be presented. Number of patients who completed the study, discontinued from the study and transferred to the OLE will also be summarised.

3. STUDY CONDUCT

3.1 RANDOMIZATION ISSUES

To maintain a balanced number of patients enrolled in each treatment arm, randomization was stratified by *APOE* status (presence or absence of $\epsilon 4$ allele) and anti-dementia medications (present or absent) at baseline, and geographic region.

3.2 DATA MONITORING

The incidence and nature of adverse events, serious adverse events, ARIA-E and ARIA-H, and laboratory abnormalities has been assessed on a regular basis by an un-blinded independent Data Monitoring Committee (iDMC). The iDMC charter describes the roles of the iDMC and the frequency and conduct of the planned review meetings.

4. STATISTICAL METHODS

In the following sections, for all continuous variables for which descriptive statistics are indicated, the following statistics will be reported: the number of observations, the mean, median, standard deviation, and minimum and maximum. The 25th and 75th percentiles (Q1 and Q3) will also be reported for selected tables.

In all analysis, baseline is defined as the last available assessment up to and including the first day of study drug intake in the double-blind period (Part 1).

4.1 ANALYSIS POPULATIONS

4.1.1 Intent-to-Treat Population

The intent-to-treat (ITT) population will include all randomized patients. The ITT analysis will be performed by randomized treatment.

4.1.3 CSF Intent-to-Treat Population

The CSF intent-to-treat (CSF-ITT) population will include all patients in the ITT who had at least one post-baseline CSF measure of $A\beta_{1-40}$, $A\beta_{1-42}$, pTau or tTau. The CSF ITT analysis will be performed by randomized treatment.

4.1.4 MRI Intent-to-Treat Population

The MRI intent-to-treat (MRI-ITT) population will include all patients in the ITT who had at least one post-baseline volumetric MRI scan or rs-fMRI scan. The MRI ITT analysis will be performed by randomized treatment.

4.1.5 Safety Follow-Up Population

The safety follow-up population will include all patients who did not enter the OLE who had a vital signs visit date, AE start date or study completion or discontinuation date greater than 28 days after their last intake of study-drug in double-blind. It will also include all patients who entered the OLE whose first dose in the OLE was greater than 28 days after their last dose in double-blind. The time each patient spent in follow-up is also defined by these dates.

4.2 ANALYSIS OF STUDY CONDUCT

4.2.1 Disposition of Patients

The number of patients randomized, and the number and percentage of patients who prematurely withdrew from the study (including the reasons for discontinuation and the distribution of these discontinuations by time-windowed visit) will be summarized using descriptive statistics.

4.3 ANALYSIS OF TREATMENT GROUP COMPARABILITY

4.3.1 Demographic Data and Baseline Characteristics

Baseline comparability of the placebo and gantenerumab treatment groups will be assessed for the Safety and ITT populations. The comparisons will be made on patient demographic and baseline variables, including the following:

- Sex
- Age
- Race
- Years of education
- Weight
- Height

- Body mass index
- *APOE* status
- MMSE, total score at baseline
- ADAS-cog (13 items) at baseline
- ADCS-ADL, total score at baseline
- CDR-SB at baseline
- CDR-Global score at baseline
- NPI at baseline

All comparisons will be based on descriptive statistics.

4.3.2 Previous and Concomitant Medications and Medical History

A patient's medical history is defined as a record of all medical events (for example: procedures and diseases) that start and finish prior to the date of the first dose of study treatment. Similarly, medications a patient has received with an end date prior to the date of the first dose of study treatment will be classified as previous medications.

Any medication ongoing on the date of the first dose of study treatment is classified as previous-concomitant, while any medication starting after the first dose of study treatment is classified as concomitant. Any medical event occurring after the first dose of study treatment is classified as an AE and handled according to the rules in Section [4.5.2](#).

If the medical event (for example: treatment, procedure or disease) does not have complete or valid start and end dates, the following rules will be applied. The reference date is defined as the date of the first dose of study treatment.

- If the medical event start date is (a) completely missing, or (b) only has the year specified and this is the same as the year of the reference date, or (c) only has the month/year specified and these are the same as the month/year of the reference date, then the medical event will be assumed to have started before the reference date.
- If the medical event end date is (a) completely missing, or (b) only has the year specified, and this is the same as the year of the reference date, or (c) only has the

month/ year specified, and these are the same as the month/ year of the reference date, then the medical event will be assumed to have ended after the reference date.

- Otherwise, partial medical start and end dates (month/year or year only) will be compared with the corresponding part of the reference date to determine whether strictly before or strictly after the reference date (no other possibility exists, because this is covered by the two previous bullet points).

All listings and summaries will include only the preferred term or super class term.

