5.3.5.9 Preexisting Medical Conditions

A preexisting medical condition is one that is present at the screening visit for this study. Such conditions should be recorded on the General Medical History and Baseline Conditions eCRF.

A preexisting medical condition should be recorded as an adverse event only if the frequency, severity, or character of the condition worsens during the study. When recording such events on the Adverse Event eCRF, it is important to convey the concept that the preexisting condition has changed by including applicable descriptors (e.g., "more frequent headaches").

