5.4 PREVIOUS AND CONCOMITANT MEDICATION AND MEDICAL HISTORY

The medical history, previous medication and concomitant medication data will be coded using the WHO Drug Dictionary version that is current at the time of the analysis (WHO Drug 1 March, 2021), and will be summarized for the SE populations by previous randomization and overall:

- Medical history is defined as a record of all medical events (for example: procedures and diseases) of a patient that started prior to the date of the first dose of study treatment in the DB part.
- Previous medication is defined as all received medications of a patient that ended prior to the date of the first dose of study treatment in the DB part.
- Concomitant medications are classified into the following four categories.
 - Medications ongoing at first dose in the DB is defined as all received medications of a patient that started prior to and were still ongoing on the date of the first dose of study treatment in the DB part.
 - Medications used after first dose in the DB is defined as all received medications of a patient used after the first dose of study treatment in the DB part.
 - Medications ongoing at first dose in the OLE is defined as all received medications of a patient that were still ongoing on the date of the first dose of study treatment in the OLE.
 - Medications used after first dose in the OLE is defined as all received medications of a patient that started after the date of the first dose of study treatment in the OLE.

If the medical event (for example: treatment, procedure or disease) does not have complete or valid start and end dates, the following rules will be applied. The reference date is defined as the date of the first dose of study treatment.

If the medical event start date is (a) completely missing, or (b) only has the year specified, and this is the same as the year of the reference date, or (c) only has the month/year specified, and these are the same as the month/year of the reference date, then the medical event will be assumed to have started before the reference date.

If the medical event end date is (a) completely missing, or (b) only has the year specified, and this is the same as the year of the reference date, or (c) only has the month/ year specified, and these are the same as the month/ year of the reference date, then the medical event will be assumed to have ended after the reference date.

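### Part 1 SAP 4.3.2 gives conditions ongoing at first dose no class, so the Part 1 medical history output omits them, and the OLE SAP defines medical history differently

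*SAP*

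**What the plan says.** Part 1 SAP 4.3.2 defines a patient's medical history as the events "that start and finish prior to the date of the first dose of study treatment". For later events it says: "Any medical event occurring after the first dose of study treatment is classified as an AE". It names no third class for medical events.

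Medications get three classes in the same section. Besides those that ended before first dose and those that started after it, "Any medication ongoing on the date of the first dose of study treatment is classified as previous-concomitant".

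The section also has a rule for incomplete dates. "If the medical event end date is (a) completely missing", or is partial and coincides with the year or month and year of first dose, "then the medical event will be assumed to have ended after the reference date".

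OLE SAP 5.4 takes medical history to be the events "that started prior to the date of the first dose of study treatment in the DB part". It sets no condition on when they ended.

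Protocol 5.3.5.9 states: "A preexisting medical condition is one that is present at the screening visit for this study". It sends such conditions to the General Medical History and Baseline Conditions eCRF and makes them adverse events only on worsening. Section 1 of the Part 1 SAP says that the SAP wording overrides the protocol.

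**The concern.** The Part 1 definition asks for two things: onset before first dose and resolution before first dose. A chronic condition that is present and stable at baseline meets the first and fails the second. It is not a new event after first dose either, so the plan has nowhere to put it.

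Such conditions are to be expected in this trial. Patients were aged 50 to 90. Protocol 4.1.2.3 excludes hypertension only when uncontrolled, 4.1.2.6 excludes HbA1c only above 8%, and 4.1.2.8 allows stable maintenance treatment for mood or anxiety disorders. Controlled active disease was therefore admissible at entry.

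What is at stake is the description of the study population. A medical history output confined to resolved events leaves out the illnesses that patients had when treatment began. The data were collected, so the loss comes from the analysis rule alone.

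**Working it through.** The plan gives no figure on this point to reproduce. The check is to sort every date pattern for a record on the medical history form under each SAP's rule. Both rules use the same reference, the first double-blind dose.

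| Start | End | Part 1 SAP 4.3.2 | OLE SAP 5.4 |
|---|---|---|---|
| Before first dose | Before first dose | Medical history | Medical history |
| Before first dose | On or after first dose | No class | Medical history |
| Before first dose | Missing | Taken as ended after: no class | Medical history |
| Before first dose | Partial, matching the reference year or month and year | Taken as ended after: no class | Medical history |
| Missing | Missing | Taken as started before and ended after: no class | Medical history |
| After first dose | Any | Adverse event | Not medical history |

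Four of the six patterns have no class in Part 1, and all four are medical history under the OLE SAP.

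The adverse event route does not recover these records. Protocol 5.3.5.9 makes a preexisting condition an adverse event only if its frequency, severity or character worsens. The missing-date rules in Part 1 SAP 4.5.2 apply to adverse event tables, so they do not bring in a record from the medical history form.

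The end-date rule needs separating into two effects. A truly ongoing condition normally has no end date, so for those records the rule restates the loss already caused by the definition. What it adds is the event that had in fact resolved but whose end date was not recorded, or was recorded only to the matching year or month.

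The OLE report cannot fill the gap for everyone. Its introduction gives 389 randomised and 230 entering the OLE:

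- in the OLE: 230 / 389 = 59.1%
- not in the OLE: 389 − 230 = 159, and 159 / 389 = 40.9%

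OLE SAP 5.4 summarises its safety-evaluable population, meaning those dosed in the OLE, so at least 159 randomised patients are described only under the Part 1 definition.

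**The case against.** The strongest reply is that little depends on this output. Medical history is not a term in the model in Part 1 SAP 4.4.1, and baseline comparisons are descriptive. This stands: no efficacy estimate changes.

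A reader might infer that the trial's comparison of the arms at baseline misses active disease. The documents do not support that. The section holding the definition is headed as treatment group comparability, and 4.3.1 says: "Baseline comparability of the placebo and gantenerumab treatment groups will be assessed for the Safety and ITT populations". But the list of variables in 4.3.1 does not include medical history, and Protocol 6.1.3 ties comparability to baseline levels of the primary and key secondary efficacy measures. Section 4.3.2 mentions listings and summaries but specifies no comparison between arms.

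Nor can one say that an imbalance in active disease would be invisible. Most of the likely conditions are drug-treated, and their treatments appear as previous-concomitant medications. What that misses is untreated conditions and the diagnoses themselves.

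It is also true that a stable preexisting condition is rightly not an adverse event, and that one that worsens is captured. The fault is only that the medical history class does not hold it.

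A reader might multiply an assumed number of conditions per patient by 389. With an assumed 1 to 4 each, that gives 389 to 1,556 records, of which only 230 to 920 could reappear in the OLE output. Nothing in the documents supports 1 to 4, so neither range is a finding.

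Finally, the two reports need not contradict each other on any shared figure, because their populations differ. The definitions are inconsistent, and that is as far as the point goes.

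**Conclusion.** The point holds as a definitional error of minor weight. Followed as written, Part 1 SAP 4.3.2 drops from the medical history output every stable condition ongoing at first dose, plus resolved events with an absent or matching partial end date. The sponsor's own OLE SAP uses the broader definition with the same reference date.

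The number of records affected cannot be computed from the documents. What can be stated is the reach: the rule applies to the whole Part 1 population, and for at least 159 of the 389 randomised patients (40.9%) no other report supplies the broader history.

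The conclusion assumes that the programs follow the SAP text. Section 1 of the Part 1 SAP leaves datasets and programs to separate documents. If those already include ongoing conditions, the outputs are sound and only the SAP wording is wrong.

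**What to change.** In Part 1 SAP 4.3.2, define medical history as all medical events that started before the first dose in the double-blind part, matching OLE SAP 5.4. Present it in two groups: *resolved before first dose* and *ongoing at first dose*. The second group parallels the class that medications already have.

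For medical history records, use the end-date rule only to choose between these two groups, so that an incomplete end date never removes a record. Leave the rule unchanged for medications, where it separates previous from previous-concomitant use. Its wording covers treatments as well as diseases and procedures, so the amended text should say explicitly that the restriction applies to medical history alone.

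The cost is a sentence or two in the SAP and a changed selection in the medical history outputs. No new data are needed.

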4.4 EFFICACY ANALYSIS

Efficacy analysis will use time-windowed visits details of which are given in the DAP Module 3. In brief, time window borders are in the middle between scheduled visit times. If more than one visit falls in a window, the visit closest to the per-protocol visit date is used. The baseline visit window includes all assessments performed on Day 1 or before and consequently, the time window for the first post-baseline visit begins on study day 2. Therefore, data collected at an early termination visit will be summarized at the appropriate time in the trial and not at Week 104.

Not all patients will reach the primary time point (Week 104) as the trial was converted to an OLE. No imputation will be performed for individuals who did not reach Week 104. However, summaries by time-windowed visit will be provided to allow comparisons between arms at earlier time points.

There may be instances when different questionnaires are performed on different study days within the time window of one visit. In such cases, the earlier study day will be used for the time to clinically evident decline endpoint.

4.4.1 Primary Efficacy Endpoint

The co-primary efficacy outcome measures are:

- The difference between Gantenerumab and Placebo treated patients in the mean change in ADAS-Cog 13 from baseline (Day 1) to Week 104 in the population of all randomized patients.

- The difference between Gantenerumab and Placebo treated patients in the mean change in ADCS-ADL from baseline (Day 1) to Week 104 in the population of all randomized patients.

For each of the co-primary endpoints, the absolute values, change from baseline and percentage change from baseline will be summarized by time-windowed visit.

In addition, the co-primary endpoints will also be analysed using a mixed model with repeated measures (MMRM). The model will use an unstructured variance – covariance matrix for the repeated measures allowing the inclusion of individuals with incomplete data. The following variables will be included in the modelling:

Dependant variable	ADAS-Cog 13 or ADCS-ADL
Independent variables	Treatment (placebo or Gantenerumab) APOE status (carrier or non-carrier) Baseline ADAS-Cog 13 or ADCS-ADL score Time (weeks relative to first dose in study) Treatment (placebo or Gantenerumab) by time (weeks relative to first dose in study) interaction

Patient, treatment and time will be treated as class variables. All data from all patients (as defined in Section 2.2) will be used, including data from Week 104/early termination visits.

A treatment-by-time interaction contrast will be used to estimate the difference between gantenerumab and placebo in the mean change from baseline at each visit. Least square means, standard errors, 95% confidence intervals will be reported for gantenerumab relative to placebo.

